**NCT02763826**

### **Specific Aims:**

Transcranial direct current stimulation (tDCS) is a non-invasive brain stimulation technique that can modulate cortical excitability of targeted brain regions. One can measure tDCS induced changes in excitability using a different noninvasive brain stimulation method - transcranial magnetic stimulation (TMS). Various studies have investigated tDCS use in stroke patients with motor impairments (cumulatively about 200 cases). Although these studies are mostly “proof of concept” with small sample size, they do suggest that tDCS may improve motor function. Before a Phase II single-center clinical trial (a R01 application) to assess the efficacy of tDCS for stroke motor recovery is launched by the applicant, two critical scientific questions need to be answered **FIRST** in order to increase the likelihood of success of clinical trial in planning.

**What is the optimal current for stroke patients?** No systematic investigation has been done to determine the most efficacious current that is both safe and tolerable for stroke patients. There is empirical evidence that tDCS with current up to 2 mA for 20-40 minutes for either single or multiple sessions can safely be administered to healthy subjects. It is probably safe for stroke patients, but there are no safety guidelines in this population. Animal studies have established a much higher safety limit (>50X) than the human protocols, but safety concerns have limited tDCS current to 2 mA for human subjects. This is a critical issue to explore because it is likely that a higher current is more efficacious in increasing cortical excitability and hence motor recovery in stroke patients.

#### **Aim 1: To determine the optimal tDCS current in stroke subjects**

The optimal current balances cortical excitability and tolerability/safety in stroke patients. We will investigate the optimal current in range of 1 mA to 4 mA. We hypothesize that 4 mA is tolerable, safe and can induce the highest level of cortical excitability in the lesional motor cortex. We will adapt the classic, gold-standard 3+3 experimental design that is commonly used to find the maximal tolerable dose in drug trials. Tolerability/safety will be investigated by monitoring clinically detectable symptoms by monitoring vital signs and surveying subjects with a questionnaire before and after stimulation, additionally by detecting subclinical neuronal injury using (1) Magnetic Resonance Imaging/Diffusion Weighted Imaging (MRI/DWI) to detect any focal ischemia; and 2) Molecular biomarkers: S100b and neuron-specific enolase (NSE) to detect neuronal injury. Cortical excitability is measured by the amplitude of motor evoked potentials (MEPs) induced by TMS from the abductor pollicis brevis muscle of the affected side.

**What is the optimal tDCS electrode montage for stimulation?** According to the theoretical model underlying the use of tDCS for stroke motor recovery, stroke causes an “interhemispheric imbalance” with decreased motor excitability in the ipsilesional hemisphere and excessive excitability in the contralesional hemisphere. This has led to studies testing the effects of anodal (excitatory) stimulation to the lesional hemisphere, cathodal stimulation (inhibitory) to the non-lesional hemisphere or combined bi-hemispheric stimulation. However, it has not been established which montage can induce the maximal cortical excitability, and eventually the maximal motor recovery.

#### **Aim 2: To determine the optimal tDCS electrode montage in stroke subjects**

We hypothesize that the bi-hemispheric stimulation with anodal stimulation on the lesional hemisphere and simultaneous cathodal stimulation on the non-lesional hemisphere induces more cortical excitability in the lesional hemisphere than either anodal stimulation on the affected hemisphere or cathodal stimulation on non-lesional hemisphere alone. We will use a randomized, complete block design in which all stroke subjects undergo each of the three electrode montages (on different days) at the current determined in Aim1. As in Aim 1, MEPs from the affected APB muscle will be recorded pre- and post- stimulation to determine the optimal montage for the maximal cortical excitability from the lesional hemisphere.

This proposal lays the scientific foundation for systematic application of tDCS in stroke recovery research. It also serves as an important bridging step between the applicant's prior training and his next milestone - a Phase II single-center clinical trial (a R01 application) to assess the efficacy of tDCS for stroke motor recovery with the optimal current and stimulation montage determined by this proposal.

## **A: Significance:**

**A1. Motor Deficits Associated with Stroke:** There are 795,000 new strokes each year in the US and stroke is a leading cause of long term disability. Motor deficit is the most common deficit after stroke. Stroke recovery strategies, such as, innovative equipment (robotic), cellular therapy, and brain stimulation (invasively or noninvasively) seek to enhance neural plasticity thereby improving function. tDCS is a portable, non-invasive brain stimulation technique that can be applied simultaneously with rehabilitation therapy with potential to improve motor function in stroke survivors.

**A2. tDCS to Augment Motor Improvement:** tDCS can modulate the excitability of targeted brain regions by altering neuronal membrane potentials resulting from low-voltage, direct current that is transmitted through the skull via surface electrodes. Behavioral effects after a single 10-40 minute stimulation session have been demonstrated to outlast the stimulation period by as long as 90 minutes. This is most likely due to the modulation of cellular NMDA-receptors and through augmentation of synaptic plasticity that requires the presence of BDNF. To date, tDCS has been tested across the world in thousands of healthy subjects and patients with various disease conditions. In 12 published studies (summarized in applicant's review), mostly "proof of concept" studies with small sample size, subjects have included about 200 stroke patients with motor deficits with current  $\leq 2$  mA. This technique shows promise of emerging as an adjunctive therapeutic tool to promote motor recovery; however, two scientific questions must be answered before it can be further tested in large phase II/III clinical trial. For example, the optimal current (dose) is not clear, nor is the electrode montage for stroke patients.

**A3. Safety and Current (Dose) Issues:** Theoretical knowledge regarding the safety and tolerability of electrical stimulation is based on physical aspect of this technique and data from both animal and healthy human studies. These data support the safety of the present tDCS protocols. Healthy subjects are exposed to "no significant risk" at currents ranging of 0.5 to 2 mA for up to 40 minutes either over a single session or multiple sessions. However, safety implications are not clear in stroke patients (i.e., subjects with a brain lesion) and there may be potential for increased risk. So far there has been no single, dedicated study to systematically evaluate the safety and tolerability of tDCS at various currents in the stroke population.

[figure not shown]
Commonly reported side effects occurred at the site where the electrodes are placed and are a minor issue: local scalp itching, tingling or burning sensations, transient headaches or stimulation-induced skin lesions or contact dermatitis. The size of the electrode pad also matters in terms of safety and tolerability. Electrode size determines current density. It is defined as current/electrode contact area. Depending on the size of the electrode (typically  $3 \times 5$  cm^2,  $5 \times 5$  cm^2 or  $5 \times 7$  cm^2), current density even at 4 mA – the highest current available for clinical research (Chattanooga Dual-Channel Iontophoresis Device), is approximately 0.11 mA/cm^2 to 0.27 mA/cm^2. This current density is considerably below the safety threshold determined by invasive stimulation technique or the safety limit (~2%) established in an animal study. While underdosing is possible, safety concerns have led researchers to avoid higher tDCS current in stroke patients. Two studies

show that 2 mA is more effective than 1 mA in enhancing cognitive effects in healthy subjects and working memory in patients with Parkinson disease. It is not clear whether there is a linear current (dose) response relationship associated with current and cortical excitability, especially when the current exceeds 2 mA. Patient protocol evolution must balance safety and current (dose). For research with tDCS, it is critically important maximal current levels not be “frozen” at an arbitrary limit of 2 mA, especially if a higher dose is tolerated and produces more excitability changes and are thus likely more effective. Without performing an initial current (dose) finding and safety study, the field risks performing clinical trials that might be ineffective or less effective, but solely because of underdosing. Rather than wasting the time and money on potentially under-dosed studies, it is important to establish this knowledge of dose effects now.

**A4. Electrode Montage for Stimulation In Stroke Patients:** The second scientific gap concerns the optimal electrode montage that is most favorable for cortical stimulation in stroke patients. The theoretical model that serves as the basis for tDCS for post-stroke motor recovery is that of “interhemispheric imbalance (**Figure 1A**)”. After a stroke, there is decreased motor activity in the ipsi-lesional hemisphere and excessive activity in the contra-lesional hemisphere, and they are associated with poor motor recovery. In efforts to correct such imbalance, tDCS was applied either by

- Anodal stimulation (Figure 1B) on the affected hemisphere to up-regulate the cortical excitability, or
- Cathodal stimulation (Figure 1C) on the non-lesional hemisphere to down-regulate the cortical excitability, or
- Bi-hemispheric stimulation (Figure 1D) with anodal stimulation on affected hemisphere and simultaneous cathodal stimulation on non-lesional hemisphere to up regulate and down regulate cortical excitability simultaneously.

**Figure 1. Schematic Model Interhemispheric Imbalance and Montage of Direct Current Stimulation**

All three electrode stimulation montages demonstrated various promising improvements in motor functions in stroke patients. Two studies with healthy subjects suggest bi-hemispheric stimulation may have advantages over uni-hemispheric stimulation. One TMS study with bihemispheric rTMS suggested that the bi-hemispheric stimulation yielded stronger effects than uni-hemispheric stimulation. It remains unclear which approach is optimal for stroke patients.

This proposal will address those two issues. We aim to solve a much needed scientific issue and to close a scientific gap by establishing safety limits and identifying the optimal current and electrode montage for stroke patients. This project defines the fundamental work needed before systematically investigating the application of the technique in promoting motor recovery in stroke patients, thereby improving the odds of success for the future clinical trial.

**B. Innovation:**

- Innovative trial design.** We innovatively adapt a 3+3 trial design (**Figure 4**) that is commonly used in drug trials to assess safety and tolerability of tDCS current for Aim 1. Current associated with tDCS technique is like dosage to a drug that can be adjustable. Evaluating safety/tolerability of tDCS technique is similar to assessing drug safety and dosing finding. While innovative, the design is simple and easy to understand as well as to implement.
- Use of MR imaging and biomarkers to test for subclinical neuronal injury.** We will test for subclinical injuries with a combination of imaging and biomarker measurements to best ensure the safety in stroke subjects, as opposed to only assessing safety and tolerability with clinically detectable symptoms as done in most of the previous tDCS safety studies. MRI Diffusion Weight Imaging, dependent on the motion of water molecules, provides information regarding tissue integrity. It is a gold standard for early detection of brain ischemia  with a high sensitivity as well as high specificity . An Apparent Diffusion Coefficient (ADC) value decrease represents diffusion restriction while an ADC value increase indicates an increase in water mobility in the stimulated cortex. Neuron-specific enolase (NSE) and S-100b protein (S-100b) are two widely investigated molecular markers for brain injury . NSE originates from the cytoplasm of neurons and neuroendocrine cells. S-100 protein is a dimeric acidic calcium-binding protein found in the brain with high concentrations in astrocytes and Schwann cells. The serum levels of these proteins are elevated after different types of brain injury including focal and global ischemia , traumatic brain injury  and hypoxic brain injury .

[figure not shown]

In summary, consistent with prior studies and consensus from experts in the field, 2 mA appears to be a safe current for stroke patients. Further, we have established the feasibility of recruiting stroke subjects and using tDCS as proposed and using TMS for cortical excitability assessment.

#### D: Approach:

This grant proposal is divided into two independent, but well-connected experiments – Aim 1 to determine the optimal *current* and Aim 2 to address the *optimal stimulation montage*.

[figure not shown]
#### Aim 1: To determine the optimal current in stroke patients

##### D1.1 Design:

This aim is a phase I type study to determine the most efficacious current for tDCS, recognizing that this current level must be tolerable and safe. The trial design is adapted from the classical, gold-standard 3+3 drug trial design, which is commonly used to find the maximal tolerable dose for a chemical drug. The main justification for this design is that the maximal tolerable current (dose) is usually and arbitrarily defined as the dose at which one-third of the patients experience current (dose)-limiting major side effects/response. The algorithm for current (dose) escalation is detailed in (**Figure 4**). The study starts with 1 mA : (a) if no major response occurs in any of the three subjects, a next current at 2 mA will be used next; (b) if major response occurs in 2-3 study subjects, then the trial will stop at this current level; (c) if major response occurs in one subject, then 3 additional study subjects will be entered to further test the safety of same current dose; if no major response occurs, then the current will be escalated next current level; if further major response occurs, then the trial will terminate. The previous current level will be defined as the maximal tolerable current (dose). The current tDCS device available on the market (Chattanooga Dual-Channel Iontophoresis Device) for research use has a maximal current of 4.0 mA. The sequence for current escalation will be 1.0 mA >> 2.0 mA >> 2.5 mA >> 3.0 mA >> 3.5 mA >> 4.0 mA.

While we vary current in this protocol, other features of the stimulation will be controlled:

- **Duration of stimulation will be 30 minutes:** Data show the increased excitability of tDCS can last as long as 90 minutes. Our rehabilitation intervention will take one hour. Thus, by using 30 minutes of

stimulation, as has been commonly used in stroke studies, we should ensure that the potentially beneficial effects of the stimulation will not wear off during the course of rehabilitation.

- **Size of electrode will be 3 × 5 cm^2:** The commonly used 3 × 5 cm^2 size pad is chosen because it is adequate to cover the the primary motor cortex – our area of interest for brain stimulation in stroke subjects to facilitate upper extremity motor function recovery.
- **Electrode montage will be bi-hemispheric stimulation :** the bi-hemispheric stimulation montage is used for Aim 1 because safety profiles can be evaluated for both anodal stimulation and cathodal stimulation on the same study subject.

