25. Note that these analyses must be completed for each set of 3 subjects in a group to determine whether one or more major responses occurred before enrollment continues. If no major response occurs, the next 3 subjects will be entered to go through procedure 9-23 according to **Figure 4**.

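### Aim 1 is framed as finding the most efficacious current, but its design can only identify the highest tolerated tested current; the conclusion should say so and the MEP data should be labelled descriptive

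*Combined protocol and SAP*

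**What the plan says.** **Objective.** D1.1 opens with "This aim is a phase I type study to determine the most efficacious current for tDCS" and adds that the level has to be tolerable and safe. The Specific Aims say "The optimal current balances cortical excitability and tolerability/safety in stroke patients" and hypothesise that 4 mA is tolerable, safe and "can induce the highest level of cortical excitability in the lesional motor cortex". D1.4 expects the largest MEP increase at 4 mA.

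**Rule.** The 3+3 algorithm in D1.1 escalates, expands or stops on major responses. The definition that follows lists second-degree burn, seizure, a new DWI lesion or reduced ADC, and discontinuation for one of these. MEP is not among them. The level below the one that stops the trial is the maximal tolerable current. Section B describes the design as adapted "to assess safety and tolerability of tDCS current for Aim 1", and the human-subjects appendix calls part 1 a tolerability study.

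**MEP analysis.** D1.3 plans a plot of MEP amplitude by current group, with no estimate, interval, model or selection criterion. Each level enrols new people. D1.2 says "If no major response occurs, the next 3 subjects will be entered".

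**Use of the result.** Aim 2 runs at the Aim 1 current. The later phase II trial is to proceed "with the optimal current and stimulation montage determined by this proposal". The D5.1 timeline gives the first manuscript as covering both efficacy and safety across current levels.

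**The concern.** The objective has two parts, efficacy and tolerability, and only tolerability has a rule. Nothing in the available text says how MEP results would choose or change the current, although the Specific Aims define the optimum as a balance of the two. An investigator who followed the plan exactly would obtain a tolerability result and could report it as an efficacy result.

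Highest tolerated cannot simply stand in for most efficacious. Section A3 says "It is not clear whether there is a linear current (dose) response relationship associated with current and cortical excitability", especially above 2 mA. The selected current is used in every Aim 2 session and in the phase II rationale, so an unsupported efficacy label would travel with it. With no stated rule, a choice between, say, 3.0 and 4.0 mA could also be made after seeing a noisy plot.

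**Working it through.** **1. The plan's own sample size.** D1.1 lists six levels: 1, 2, 2.5, 3, 3.5 and 4 mA. With no major response, 6 × 3 = 18. If every level is expanded, 6 × 6 = 36. Stopping at the first level gives 3. D1.3's predicted 18 and range of 3 to 36 reproduce. The plot therefore has 3 different subjects per level in the expected case and 6 at most.

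**2. Assumptions for MEP.** The available text gives no Aim 1 MEP SD, effect or alpha. Effects below are in between-subject SDs, with all six levels passing and two-sided 0.05. The value 0.85 is borrowed from Aim 2 (D2.3), where it is a paired effect. The two scales agree only at a within-subject correlation ρ of 0.5, because the between-subject equivalent is 0.85 × √(2(1 − ρ)): 1.01 at ρ = 0.3 and 0.38 at ρ = 0.9. It is one point in a range.

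**3. Where would the plot peak?** Level means are taken as normal with variance 1/n, and the chance that a given level has the highest mean is computed. No section adopts a highest-mean rule; this only shows how far the plot can be trusted.

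| True pattern | n per level | Event | Chance |
|---|---|---|---|
| No effect | 3 | 4 mA highest | 17% |
| Linear, +0.85 SD from 1 to 4 mA | 3 | 4 mA highest | 35% |
| Linear, +1.7 SD | 3 | 4 mA highest | 50% |
| Linear, +2 SD | 3 | 4 mA highest | 55% |
| Linear, +3 SD | 3 | 4 mA highest | 68% |
| Only 4 mA raised, +0.85 SD | 3 | 4 mA highest | 60% |
| Plateau from 2 mA, +0.85 SD | 3 | 4 mA highest | 20% |
| Peak at 3 mA (+0.85 SD, half left at 4 mA) | 3 | 3 mA highest | 34% |
| Linear, +0.85 SD | 6 | 4 mA highest | 42% |
| Only 4 mA raised, +0.85 SD | 6 | 4 mA highest | 78% |

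**4. Precision of 4 mA versus 1 mA.** The 95% half-width with pooled SD is t × √(2/n).
- n = 3: 2.179 × √(2/3) = 1.78 SD.
- n = 6: 2.042 × √(2/6) = 1.18 SD.

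**5. Trend across all levels.** The mean dose is 16/6 = 2.667, and the squared deviations of the six doses sum to 5.833. Sxx is therefore 3 × 5.833 = 17.5 for 18 subjects and 35 for 36.
- The half-width of the slope over the 3 mA range is t × 3/√Sxx. For 18 subjects it is 2.120 × 0.717 = 1.52 SD; for 36 it is 2.032 × 0.507 = 1.03 SD.
- Power for a total rise D uses the noncentral t with noncentrality (D/3)√Sxx. With 18 subjects, D = 0.85 gives 1.185 and 20% power, D = 2 gives 2.789 and 74%, and 80% needs D = 2.14. With 36 subjects, D = 0.85 gives 37%, and 80% needs D = 1.46.

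**6. Would a straight-line slope answer the question?** The expected fitted slope over 3 mA is 3 × Σ(deviation × mean)/5.833.
- Plateau from 2 mA: 3 × 0.85 × 1.667/5.833 = +0.73 SD.
- Peak at 3 mA with means 0.85 × (0, 0.5, 0.75, 1, 0.75, 0.5): 3 × 0.85 × 1.167/5.833 = +0.51 SD.
- Truly linear: +0.85 SD.

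All three are positive, and they cannot be told apart with a half-width of 1.52 SD.

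**The case against.** The strongest reply is that this is a phase I study with ambitious grant wording. D1.1 qualifies its objective at once with tolerability and safety, the 3+3 procedure is clearly written out, and its output is named correctly. Because D1.3 plans no MEP test, the analysis is already descriptive in practice. This stands as to the procedure, and neither the escalation rule nor the small cohorts are faulted here. It does not rescue the conclusion, because the efficacy half of the objective has no rule and section A3 leaves the dose response open.

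The power figures are also assumption-driven. That stands. Figure 4 and some text ahead of the preliminary-evidence summary are not in the copy reviewed, so the absence of an MEP SD is not held against the plan. D1.1 describes the Figure 4 algorithm in words.

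Three stronger readings are tempting, and the documents do not support them.
- *The MEP data are uninformative in either direction.* This is too absolute. With a 2 SD rise the trend test has 74% power, although 4 mA would still plot highest in only 55% of trials.
- *Tolerability alone fixes the Aim 2 current, so MEP must be barred from the choice.* No available sentence says this, and the Specific Aims speak of a balance. Excluding MEP is a trade-off for the sponsor to weigh.
- *Aim 1 analyses the wrong MEP quantity.* D1.3 names amplitude, but D1.4 speaks of an increase, so a change measure is probably intended. It only needs naming.

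**Conclusion.** The point holds in this form: Aim 1 claims a property that its design does not have. The design can yield the highest tolerated tested current. If no major response occurs up to 4 mA, that result is the device's ceiling and not an observed limit of tolerance. The design cannot rank currents on efficacy unless the MEP effect is very large, illustratively about 2 between-subject SDs or more from 1 to 4 mA for roughly 75 to 80% trend power with 18 subjects. Even a detected trend would not locate the best level.

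The textual conclusion rests on the stated rule and the stated analysis and needs no assumption about MEP variability. The percentages do rest on such assumptions and indicate scale only. Participant safety rules are unaffected. The change should be made because the Aim 1 result sets the Aim 2 current and supports the phase II rationale.

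**What to change.** 1. **Conclusion.** Report the Aim 1 result as the highest tolerated tested current. Drop the efficacy and optimality wording from that conclusion and from the justification of the Aim 2 current.
2. **D1.3.** Analyse the post/pre MEP quotient that D2.3 already uses. Show each subject's value by level, with level means and 95% CIs, labelled descriptive. With 3 subjects and that level's own SD, the half-width is 4.303/√3 = 2.48 SD, so the individual values matter most. A straight-line slope should not be the main summary, because it stays positive under a plateau or a mid-range peak.
3. **Choice of the Aim 2 current.** State the rule before any Aim 1 data are seen. The default would be the highest level that passes 3+3 (0 of 3, or 1 of 6, major responses). The sponsor may instead prespecify a rule that balances MEP gain against tolerability, in keeping with the Specific Aims.

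The cost is protocol wording and a fuller display of data already collected. Subjects, visits, escalation and stopping rules do not change. The downside is a more modest Aim 1 claim. Under the default rule, 4 mA could also go forward even if excitability plateaus or falls at high current.
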